5.2 Recruitment, Consent, Screening and Enrollment

Participants will be recruited through IRB-approved recruitment materials (to include flyers, posters, newspaper ads and radio scripts). Volunteers interested in the study will be invited and scheduled to a briefing session at their convenience. Briefing sessions will be conducted by the Principal Investigator (PI) or designee at the MUWRP facility at regular intervals throughout the recruitment phase. The briefing session will be followed by an opportunity for questions from the volunteers. All volunteers interested in this study will subsequently, individually be administered informed consent.

5.2.1 Consent Procedures and Screening

The PI or their designee will review the consent form in detail with potential participants and answer any questions. Written informed consent will be obtained from each participant before any study procedures are performed. All informed consent forms will be administered individually, in a private setting, with strict respect of confidentiality. Participants will be given ample time and opportunity to inquire about details of the study, discuss with close family members or friends and ask any questions before dating and signing the consent forms. A copy of the signed informed consent form will be given to the participant along with a copy of the volunteer event schedule (Appendix 3). The consenting process will be documented in the case report forms (CRFs).

After providing signed informed consent the volunteer will complete an Assessment of Understanding (AoU). Volunteers are allowed to take the AOU three times, but must have a passing score of 90% or greater by the third attempt to participate in the study. If after 3 attempts to pass the AOU the volunteer is unable to do so, the volunteer will become ineligible for study participation.

Volunteers who have passed the AoU and have given written informed consent will undergo a complete medical history, physical examination, and screening laboratory assessments to determine eligibility for trial participation. The following screening assessments will be completed after the informed consent process has been completed:

- Medical history
- Physical exam
- Vital signs and weight
- Serum pregnancy test for all females
- CBC with total lymphocyte count
- Creatinine
- ALT

- HIV testing (including pre/post-test counseling), and referral as appropriate
- Syphilis serology testing
- Pre-existing vector immunity testing
- Peripheral blood mononuclear cells (PBMC) and plasma for storage

Screening evaluations for specific eligibility criteria must be completed within the screening visit window specified (Appendix 1) prior to enrollment, but may be repeated one time within the screening visit window, if the initial laboratory result is not deemed medically significant in the clinical judgment of the investigator, in order to confirm eligibility. Counseling on the potential risks of becoming pregnant during this trial will be provided. Pre-HIV test counseling and post-HIV test counseling will be provided during the screening process.

Study volunteers may be scheduled for a second Screening Visit to evaluate laboratory and test results if an abnormality or illness had been identified at the first screening. This approach will allow study staff to evaluate the recovery from any illness identified at the first screening as well as to repeat screening laboratory tests that were abnormal at the first screen due to transient illness.

The PI or Investigator at the site may discover an illness or condition, which requires treatment for the volunteer. The site will provide basic care and treatment as per National guidelines and refer these subjects to an appropriate healthcare facility for further evaluation and treatment.

Eligible and willing volunteers will be scheduled for an appointment for enrollment and the initial vaccination visit within 56 days of having satisfied eligibility requirements.

5.2.2 Day 0 Through Week 48

Day 0 is defined as the day of enrollment and study injection. Study eligibility criteria are reviewed on Day 0 as part of the enrollment process. If clinical assessment on Day 0 suggests significant changes may have occurred since the screening visit, then the physical examination, hematology tests, and blood chemistries done at screening must be repeated, as appropriate, before the participant can receive a study vaccination. Pregnancy test results for women of childbearing potential must be obtained prior to the study injection. Day 0 evaluations immediately prior to the first injection are the baseline for subsequent safety assessments.

Refer to the table in Appendix 1 for details on the Schedule of Evaluations and the window(s) permitted. After Day 0, deviations from the visit windows in completing study visits are discouraged and will be recorded as protocol deviations, but are permitted, at the discretion of the PI (or designee), in consultation with the sponsor, in the interest of obtaining participant safety and immunogenicity evaluations following exposure to the investigational vaccine.

Study visit procedures and tests through Week 48 include the following as indicated in the SOE (Appendix 1):

1. Signature of study participation informed consent form
2. AOU (prior to enrollment)
3. Clinical evaluations: vital signs; targeted physical examination on any visit if indicated by interim complaints or laboratory findings
4. Interim medical history, including any new medications taken

5. Counseling on avoidance of pregnancy
6. Post-injection vital signs and assessment of injection site at 30 to 60 minutes post-injection (with target of 30 to 45 minutes, when possible)
7. Diary Card: In the evening on the day of injection; 7-days for self-assessment by participant
8. Urine pregnancy test for females of reproductive potential
9. CBC, total lymphocyte count, platelet counts
10. Blood creatinine and ALT
11. HLA Type
12. Serum, PBMCs, and plasma for protocol assessments, including intracellular RNA and archiving

Stored samples with consent for genetic testing may be used to elucidate genetic factors associated with immune response to a vaccine and to further evaluate responses to the vaccine. Results from genetic testing will not be provided to participants as the results are not validated for clinical use. Any remaining cells, serum, or plasma will be stored at the NIAID Vaccine Immunology Program (VIP) for future exploratory virological and immunological assays as per individual participant's consent for future use.

5.3 Administration of the Study Injection and On-Study Assessments

Injections will be administered IM in a 1 mL volume by needle and syringe. It is recommended, but not required, that the injection be administered into the non-dominant arm. When choosing an arm for the injection, clinicians should consider whether there is an arm injury, local skin problem or significant tattoo that precludes administering the injection or will interfere with evaluating the arm after injection.

Following the study injection, participants will be observed for a minimum of 30 minutes. Vital signs (temperature, blood pressure, and pulse) will be taken 30 to 60 minutes post-injection (target of 30 to 45 minutes). The injection site will be inspected for evidence of local reaction during this period. In keeping with good medical practice, acute medical care will be provided to participants for any immediate allergic reactions or other injury resulting from participation in this research study.

5.3.1 7-Day Solicited Reactogenicity

Temperature and solicited local and systemic signs/symptoms will be recorded in the clinic prior to vaccination and at a minimum of 30 minutes post injection and then daily by the participant for 7 days.

Participants will be given a "Diary Card", a thermometer, and a ruler. The diary card will be used as a memory aid, on which the participant will record temperature, local and systemic symptoms and concomitant medications daily for 7 days after the injection. Participants will be trained to complete the paper diary card, how to use the thermometer, and how to measure injection site swelling and redness using the ruler. Completion of the diary card training will be noted in source documents. The written (paper) diary card will be transcribed into the study database and will be stored in the participant file for monitoring purposes.

The solicited signs and symptoms on the diary card (among others) will include: joint pain, malaise (feeling unwell), myalgias (muscles aches other than at injection site), headache, chills, nausea, and pain at injection site. Where multiple assessments are taken on the same day, participants will be requested to record the day's highest measured temperature and measurement of largest diameter for redness and swelling at the injection site. The completed diary cards are collected at the first visit following completion of the 7-day diary card (about 2 weeks after the injection).

Follow-up on participant well-being will be performed by telephone or clinic visit on the day following vaccination and by clinic visit on Day 3 following the injection to assess their clinical status. Participants may call or come to the clinic at any time-point for evaluation, if they experience unusual, moderate or severe signs and symptoms. Diary cards will be reviewed with the clinician at any visit from day of vaccination through the first study visit following completion of the diary card. If upon reviewing the clinician finds that general symptom or injection site symptom information (except swelling or redness measurements) is missing from the diary cards, the participant will be asked to provide the missing information to the best of their recollection.

At every visit through study day 28, all participants will be asked about other interim adverse experiences, which will be recorded in source documents and entered into the study database within 3 business days. After study day 28, only serious adverse events and new chronic medical conditions that require ongoing medical management will be recorded in source documents and entered into the database, through the last study visit. All other adverse events will be recorded on source documents only. The PI or designee will assess the relationship of the study product to the events.

5.3.2 Management of Reactogenicity Adverse Events Following Study Vaccinations

Participants will be informed that a fever of 38.5°C (Grade 2) or higher lasting greater than 24 hours, rash, urticaria, or significant impairment in the activities of daily living (ADL) should prompt a visit to the clinic. Fever less than 38.5°C or lasting less than 24 hours may prompt a clinic visit at the discretion of the study clinicians. Any condition which in the judgment of the clinician should be evaluated clinically or by laboratory testing would require a clinical visit. Participants are permitted to initiate an unscheduled clinic visit at their discretion but these visits will be compensated as per Section 10.5.

5.3.3 Management of Laboratory Abnormalities After Vaccination

If any lab result is a Grade 3 or Grade 4, then repeat testing of the abnormal test will be performed within 48 hours. The specific timing of repeat testing for a Grade 2 laboratory test change will be determined by the study clinicians as medically appropriate.

5.4 Concomitant Medications

Current concomitant medications are recorded in the study database at enrollment and for 7 days post-vaccination. Subsequently, concomitant medications will be updated in the study database if there is an occurrence of an adverse event that is considered related to the IP or that requires expedited reporting or development of a new chronic medical condition that requires ongoing medical management.

Clinicians should discuss with study participants with regard to the timing of FDA or locally-approved vaccines. Receipt of a licensed vaccine during study participation will be recorded in the study database. Otherwise, a record of other concomitant medication changes throughout the study will not be recorded in the study database.

5.5 Study Discontinuation

The study may be stopped or cancelled at any time by decision of the PI, Walter Reed Army Institute of Research (WRAIR) IRB, the United States Army Medical Research and Development Command's (USAMRDC) Office of Research Protections (ORP), Human Research Protection Office (HRPO), NIAID, the U.S. FDA, U.S. DoD, the Office for Human Research Protection (OHRP), Uganda National Drug Authority (NDA), Uganda National Council of Science and Technology (UNCST), or the Makerere University School of Public Health (MUSPH) IRB. The PI will notify the IRB in writing of any stoppage or cancellation of the study.

5.5.1 Early Discontinuation or Withdrawal of Study Participants

A participant will be taken out of the study entirely under the following circumstances:

- Repeated failure to comply with protocol requirements
- Participant requests withdrawal
- Participant develops a medical condition that is a contraindication to continuing study participation
- The PI assesses that it is not in the best interest of the participant to continue participation in the study

Each participant has the right to withdraw from the study at any time for any reason without affecting the right to treatment by the investigator. The investigator should make an attempt to contact participants who did not return for scheduled visits or follow-up. Although the participant is not obliged to give reason(s) for withdrawing prematurely, the investigator should make a reasonable effort to ascertain the reason(s) while fully respecting the participant's rights.

Any participant who withdraws consent will not have any further data collected after consent has been withdrawn. However, samples and data that were collected prior to a participant's withdrawal of consent will be used/included in sample and data analysis.

If a participant withdraws from the study prior to receiving the study injection, the next available participant will be placed in the vacated slot. Participants who withdraw prior to receiving the study injection will not count toward the total participants enrolled in the study. Replacements for participants who withdraw from the study after receiving the study injection are not permitted.

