3.0 ENDPOINTS

3.1 Primary Endpoints: Safety

Assessment of product safety will include clinical observation and monitoring of clinical chemistry and hematology parameters. Safety will be closely monitored after injection and evaluated through 48 weeks after the study injection. The following parameters will be assessed:

- Occurrence of solicited local reactogenicity signs and symptoms for 7 days following the vaccination
- Occurrence of solicited systemic reactogenicity signs and symptoms for 7 days following the vaccination
- Change from baseline for safety laboratory measures
- Occurrence of adverse events of all severities through 28 days after the study injection
- Occurrence of serious adverse events and new chronic medical conditions through the last study visit

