7.6 Reporting Serious and Unexpected Adverse Events

7.6.1 Study Reporting Period for SAEs

The protocol-defined expedited event reporting period is 48 weeks after study agent administration (study completion) or discontinuation of the participant from study participation for any reason. After the end of the protocol-defined SAE Reporting Period stated above, sites must report suspected unexpected serious adverse reactions (SUSARs) if the study site staff becomes aware of the event from a participant on a passive basis (i.e., from publicly available information).

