The participant may terminate participation in the study at any time for any reason without penalty. Additionally, in the event that the participant is unable or unwilling to adhere to the protocol design, the investigator may terminate their participation for safety purposes.

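### After the single injection, removal for reasons other than withdrawn consent leaves no active collection of a later, new SAE or chronic condition, yet the participant stays in the denominator (cheap improvement, probably small effect)

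*Combined protocol and SAP*

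**What the plan says.** Sections 4.0 and 6.1 give each participant one injection, on Day 0. Section 5.5.1 then says: "A participant will be taken out of the study entirely under the following circumstances". The grounds are repeated non-compliance, the participant's request, a medical ground ("Participant develops a medical condition that is a contraindication to continuing study participation") and the investigator's view of the participant's best interest. Section 10.3 adds that, for a participant unable or unwilling to adhere, "the investigator may terminate their participation for safety purposes". Section 5.5.1 stops data collection expressly in one case only: "Any participant who withdraws consent will not have any further data collected after consent has been withdrawn". It does not allow replacement after injection.

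Section 7.6.1 sets the expedited reporting period at 48 weeks after injection "or discontinuation of the participant from study participation for any reason". Its next sentence begins "After the end of the protocol-defined SAE Reporting Period stated above" and requires SUSARs to be reported "if the study site staff becomes aware of the event from a participant on a passive basis".

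Section 3.1 says safety will be "evaluated through 48 weeks after the study injection". Its endpoint for SAEs and new chronic conditions runs to the last study visit, as does the recording rule in 5.3.1. Section 8.2.1 expresses safety events as proportions of participants, and section 8.3 analyses everyone vaccinated. Section 8.3.2 asks for a detailed listing of adverse events, but not for the length of safety follow-up. It gives no rule for participants whose safety follow-up is incomplete.

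**The concern.** Once the injection has been given, leaving the study can only end observation. For a participant removed without withdrawing consent, the plan contains no step that looks for a new SAE or new chronic condition between removal and Week 48. Such an event is counted only if the site happens to hear of it, while the participant still counts in the denominator as one without an event.

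The error runs one way, because an unseen first event lowers the observed proportion and cannot raise it. The loss may also be related to health, since two of the grounds concern a medical condition or the participant's interest. At stake is how the 48-week proportion with SAEs or new chronic conditions can be read. A reader of the report could not tell 0/20 fully observed from 0/20 partly observed. The staged enrolment reviews and the pause rules are largely unaffected.

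**Working it through.** **1. Does another provision actively find a later, new event?**
- 5.5.1, contact attempts: these cover missed visits and are not said to continue after removal.
- 7.2, follow-up to resolution or stability: this covers events already open.
- 5.6 (pregnancy) and 5.7 (incarceration): follow-up or safety contact is kept, but only in those situations.
- 7.6.4 and 7.6.5, onward reporting of SAEs: these operate once the site is aware.
- 10.6, care for research injury: this depends on the participant coming forward.

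None does. A removal trigger that was itself an SAE or new chronic condition is already recorded, so the gap is confined to later, new events.

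**2. The plan's own precision.** With no events, the exact (Clopper-Pearson) upper 95% limit is 1 − 0.025^(1/n).
- n = 20: 16.84%
- n = 40: 8.81%

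Both match Table 4 (16.8% and 8.8%).

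**3. Limit among those fully observed.** The documents give no removal rate, so one or two per group is an assumption.
- One of 20 removed, 0/19: 17.65%, given as 17.6%
- Two of 20 removed, 0/18: 18.53%
- Pooled, one or two of 40 removed: 0/39 = 9.03%, 0/38 = 9.25%

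The shift is about 0.8 or 1.7 percentage points per group and 0.2 or 0.4 pooled.

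**4. Chance of seeing at least one event.** For an illustrative true rate of 5%, this is 1 − 0.95^n: 64.2% (n = 20), 62.3% (19), 60.3% (18). It treats a removed participant as contributing nothing, which overstates the loss.

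**5. Outer bound.** Suppose no event is seen but every removed participant had one. A reported 0/20 (limit 16.8%) would truly be 1/20 (24.9%) with one removed, or 2/20 (31.7%) with two. If all participants share one risk q, the chance of that pattern is:
- one removed: q(1 − q)^19, at most 0.05 × 0.95^19 = 1.9%
- two removed: q²(1 − q)^18, at most 0.10² × 0.90^18 = 0.15%

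**6. Observation time exposed.** From Appendix 1, if visits stop at removal:
- after the Day 28 visit, (336 − 28)/336 = 92% of the period and four visits (Days 56, 112, 168, 336) are lost
- after the Day 168 visit, (336 − 168)/336 = 50% and one visit are lost

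**7. How a sensitivity analysis should count.** Suppose one participant has a recorded event and is then removed, and all others are fully followed. All vaccinated gives 1/20 (limit 24.9%). Restricting to fully followed participants gives 0/19 (17.6%), which deletes a real event. If a second participant, without an event, is also removed, dropping only that second person gives 1/19 (26.0%) and keeps the event.

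**The case against.** The strongest reply is that the end of contact is an inference. No sentence says that visits or calls cease, and 5.5.1 bars data collection only on withdrawn consent. Section 7.6.1 governs expedited reporting, whereas database recording is set by 5.3.1 and 7.2, and 7.2 names no stop at discontinuation. This stands, and the point is worded accordingly: the gap comes from reading 5.5.1 and 7.6.1 together.

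A reader might go further and infer that contact after removal is prohibited, or that an SAE which is not a SUSAR has no route at all. The documents support neither. Section 7.6.4 requires every SAE, whatever its relationship, to go to the IRB and the national drug authority once the site is aware, and 7.6.5 covers related SAEs and all deaths. What is missing is a step that makes the site aware.

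A reader might also see a contradiction between 48 weeks in 3.1 and discontinuation in 7.6.1. Because the endpoint bullet and 5.3.1 run to the last study visit, which can be read as ending at removal, this is a tension in wording only.

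Other mitigating facts are that availability to Week 48 and acceptance of home visits are entry conditions (4.1.1), and that several routes to lost contact are covered elsewhere. The consent forms are not in the review copy, so any follow-up they describe could not be checked. The numerical effect is modest. These facts limit the size of the problem but do not supply the missing step.

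**Conclusion.** The point holds as a cheap improvement with a probably small effect. After a removal that is not a withdrawal of consent, the plan has no active collection of a new SAE or new chronic condition, and it keeps the participant in the denominator of a 48-week safety evaluation. With one or two of 20 removed, which is an assumption, the zero-event upper limit among those fully observed is 17.6% or 18.5% rather than 16.8%. The 24.9% and 31.7% figures are bounds and should not be read as expected values. The conclusion rests on reading complete removal together with the 7.6.1 cut-off as ending scheduled contact, and on the consent forms not providing otherwise.

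**What to change.** Leave the grounds for removal as they are and align 3.1, 5.5.1 and 7.6.1. State that, after the injection, removal for any reason other than withdrawn consent ends research procedures but not collection of SAE and new-chronic-condition data. That collection continues to Week 48, by telephone if needed. End the SAE reporting period at Week 48 or at withdrawal of consent. The protocol already keeps follow-up in pregnancy (5.6) and safety contact during incarceration (5.7), so the approach is not new to it.

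In 8.3.2, report per group the number with incomplete safety follow-up, including those who withdrew consent, and their last contact week. Keep the all-vaccinated analysis with every recorded event as the main result. Do not use a table limited to fully followed participants. If a sensitivity analysis is wanted, exclude from the denominator only those with incomplete follow-up and no recorded event.

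The cost is protocol wording, matching consent text, a short addition to the safety tables and a few telephone calls. Some removed participants, particularly those removed for non-compliance, may not be reachable, so the follow-up count is needed in any case.
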